11. INTERIM ANALYSES AND DATA MONITORING

11.1 Sample Size Re-estimation

An unblinded interim analysis for sample size re-estimation will be conducted when approximately 50% of the first 350 subjects have been randomized and have either completed the 12-week treatment period or have discontinued from treatment early. The planned interim assessment will be conducted by an IDMC. An unblinded statistician who will not be part of the study team will provide results of the interim analysis to the IDMC members. Members of the IDMC will not participate in the Data Safety Monitoring Board (DSMB) and will not be members of the study team. During the interim assessment, the study team will remain blinded to the data; however, the IDMC will receive unblinded summary results to implement the decision rule for sample size re-estimation. The IDMC will only communicate the decision either to keep the original sample size or to increase it; no other results will be provided to blinded staff. The DSMB will be made aware of the decision, but not given the results that were the basis of the decision.

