8.4 Interim Analysis

8.4.1 Sample Size Re-estimation

An unblinded interim analysis for sample size re-estimation will be conducted when approximately 50% of the first 350 patients have been randomized and have either completed the 12-week Double-blind Treatment Period or have discontinued from double-blind treatment early. The planned interim assessment will be conducted by an IDMC. An unblinded statistician who will not be part of the study team will provide results of the interim analysis to the IDMC members. Members of the IDMC will not participate in the DSMB and will not be members of the study team. During the interim assessment, the study team will remain blinded to the data; however, the IDMC will receive unblinded summary results to implement the decision rule for sample size re-estimation. The IDMC will only communicate the decision to either keep the original sample size or to increase it; no other results will be provided to blinded staff. The DSMB will be made aware of the decision, but not given the results that were the basis of the decision.

[REDACTED]

- [REDACTED]

- [REDACTED]

- [REDACTED]

- [REDACTED]

- [REDACTED]

- [REDACTED]

[REDACTED]

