8.1.3 Multiplicity Handling

The efficacy of CR845 0.5 mcg/kg compared to placebo in pivotal phase 3 study CLIN3102 will be evaluated based on 1 primary and 3 secondary efficacy endpoints.

Testing of the primary efficacy endpoint will be 2-sided and conducted at the 5% error level. The study will be considered positive if the null hypothesis of no treatment difference in the primary efficacy analysis of the primary endpoint (proportion of subjects achieving ≥ 3 -point improvement from baseline with respect to the Worst Itching Intensity NRS at Week 12 of the Double-blind Treatment Period) is rejected in favor of the alternative that subjects randomized to CR845 experience significantly less itching compared to subjects randomized to placebo.

To protect the Type 1 error, a gate-keeping strategy will be implemented. Although the p-values corresponding to the hypothesis testing of the secondary variables will be reported, they will only be considered inferential if the primary analysis is statistically significant. Testing of the 3 secondary efficacy endpoints will be performed sequentially at a 2-sided 5% error level. The difference between CR845 0.5 mcg/kg and placebo with respect to the 5-D Itch total score will be tested first using the ANCOVA approach in section [8.2.4.3](#). If results are statistically significant in favor of CR845, testing with respect to the Skindex-10 total score will be conducted, also using ANCOVA. The proportion of subjects achieving ≥ 4 -point improvement from baseline with respect to the weekly mean of the daily 24-hour Worst Itching Intensity NRS at Week 12 of the

Double-blind Treatment Period will be tested only if the results of Skindex-10 total score are statistically significant in favor of CR845.

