8.2.2 Primary Efficacy Analysis

In the primary efficacy analysis, missing NRS data at the end of Week 12 will be imputed using a multiple imputation (MI) approach, assuming that subjects who discontinue double-blind treatment early would have similar Worst Itching Intensity NRS scores as other subjects in their respective treatment arm who have complete data:

- Intermittent missing NRS scores will first be imputed using the Markov Chain Monte Carlo (MCMC) method implemented with the SAS MI procedure, which is appropriate for non-monotonic missing data.
- The monotone missing NRS values will then be multiply imputed with the SAS MI procedure using the monotone regression method.

- For each stage, MI will be performed within treatment group with covariates for baseline NRS score, both randomization stratification factors, and the non-missing NRS scores for each week. Should convergence issues occur due to small cell size for the categorical covariates at either stage, those covariates will be removed from the model.
- The proportion of subjects who have an improvement from baseline with respect to the weekly mean of the daily 24-hour Worst Itching Intensity NRS score ≥ 3 points will be calculated for each imputed dataset. Differences between CR845 0.5 mcg/kg and placebo with respect to the primary endpoint will be compared using a logistic regression model containing terms for treatment group, baseline NRS score, use of anti-itch medication during the week prior to randomization, and presence of specific medical conditions.
- Twenty imputations will be performed.
- Results of the logistic regression on the multiply imputed data sets will be summarized by the SAS MIANALYZE procedure.

The observed number and proportion of subjects with ≥ 3 -point improvement among the non-imputed data will be reported along with the imputed data logistic regression model-based estimates of the proportions of responders, odds ratio, 95% confidence intervals (CIs), and p-value.

Sample size adjustment

The above MI process will be implemented completely independently among subjects contributing the interim results and those following the interim analysis. Likewise, the logistic regression and results described above will be generated independently for both samples, with the samples combined and adjusted as follows:

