The final p-value will be calculated using the Cui, Hung, Wang (CHW) procedure where the z-score is a weighted average of the z-score at the interim and the z-score observed for data collected after the interim, following the formula below:

$$Z_{CHW} = Z_{interim} * \sqrt{(n/N)} + Z_{post-interim} * \sqrt{(1 - n/N)}$$

where n is the number of randomized subjects at the interim and N is the initial number of subjects planned (350).

The adjusted odds ratio estimate prior to exponentiating and the 95% CI will be obtained using methodology suggested by Hung and Lawrence:

$$\hat{\delta} = \frac{r_1 \hat{\delta}^{(1)} + \sqrt{1 - r_1} \sqrt{N^* - r_1} \hat{\delta}^{(2)}}{r_1 + \sqrt{1 - r_1} \sqrt{N^* - r_1}}$$

where

$r_1 = n/350$

$N^* = (\text{Re-estimated total sample size})/350$

$\hat{\delta}^{(1)}$ = Least square mean difference from stage 1 analysis

$\hat{\delta}^{(2)}$ = Least square mean difference from stage 2 analysis

$$95\% \text{ CI} = \hat{\delta} \pm \left(\frac{\hat{\delta}}{Z_{CHW}} * 1.96 \right)$$

Note that it is possible for Z_{CHW} and δ to have opposite directions, particularly when close to zero, in which case the absolute value of the ratio will be used in the above formula.

See Section [11](#) for further details on the interim analysis.

The primary analysis and each sensitivity analysis will also be performed using the full combined dataset with the missing data imputed separately for interim subjects and post-interim subjects. No CHW adjustment will be conducted. Presentation of results will start with these analyses (additionally including the CHW results) and then follow with the results of the analysis from each individual stage.

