Multiple imputation with mixed missing data mechanisms (MNAR for a CR845 and MAR [missing at random] for placebo) will be used to assess the robustness of the MAR assumption. This sensitivity analysis is to investigate the departure from MAR assumption by progressively decreasing the treatment differences with respect to the NRS scores over the missing visits in active treatment group until conclusion from the primary analysis is overturned. This will be applied to only Week 12 values. The MI procedure includes the following steps:

- Intermittent missing NRS scores will first be imputed using the MCMC method with the SAS MI procedure, which is appropriate for non-monotonic missing data.
- The monotone missing NRS values will then be multiply imputed with the SAS MI procedure using the monotone regression method.
- For each stage, MI will be performed within treatment group with covariates for baseline NRS score, both randomization stratification factors and the non-missing NRS scores for each week. Should convergence issues occur due to small cell size for the categorical covariates at either stage, those covariates will be removed from the model.
- For subjects in the active treatment group, a shift parameter running from 0 to 5 points in .25 point increments in PROC MI will be progressively applied to impute the missing data at Week 12, until the p-value is >0.05 .
- This sensitivity analysis will not be performed should the initial primary results fail to achieve significance

To evaluate the potential impact of the interim analysis on the properties of statistical inference at the end of the trial, the primary and sensitivity analyses of the primary endpoint will also be presented separately for the sample of subjects enrolled into the study before and after the interim analysis.

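### The SAP gives no single rule for which subjects form stage 1 or for n in the CHW weight; read by completed-or-discontinued status, stage 1 over-represents early discontinuers

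*SAP*

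**What the plan says.** Four statements bear on who belongs to which stage.

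- **Timing.** SAP 11.1 places the interim at the point where about half of the first 350 subjects are randomized and "have either completed the 12-week treatment period or have discontinued from treatment early". Protocol 8.4.1 has the same trigger: "when approximately 50% of the first 350 patients have been randomized and have either completed the 12-week Double-blind Treatment Period", or have stopped early.
- **Analysis split.** SAP 8.2.2 runs the multiple imputation, and likewise the logistic regression, "completely independently among subjects contributing the interim results and those following the interim analysis". The protocol's Statistical Appendix uses the same split, conditional on a sample size increase.
- **CHW weight.** The SAP 8.2.2 formula applies the square root of n/N to the interim z-score, "where n is the number of randomized subjects at the interim and N is the initial number of subjects planned (350". The adjusted odds ratio uses the same ratio, r1 = n/350.
- **Display.** SAP 8.2.3 has the primary and sensitivity analyses "presented separately for the sample of subjects enrolled into the study before and after the interim analysis".

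No visible sentence assigns a subject who is randomized but still on treatment at the cut, and none says that stage 1 is the first 175 randomized.

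**The concern.** Take a subject randomized five weeks before the cut. If that subject has discontinued, status is resolved and the subject can contribute to the interim. If still on treatment, the subject cannot. When stage 1 is everyone resolved at the cut, stage membership depends on a post-randomization outcome: stage 1 gains early discontinuers and stage 2 loses them.

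At stake are the one-time decision between 350 and 500 subjects, taken on data with more missing Week 12 values than the trial will have; the stage-specific estimates that are displayed and combined; and Sensitivity 1, which counts discontinuers as nonresponders and is also combined by CHW.

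The definitions also conflict. A subject on treatment at the cut is outside stage 1 by contribution, yet is counted in n and falls on the before side of the display. Stage 1 would then be weighted as if it held more subjects than it does.

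**Working it through.** **Plan's own figures.** The documents give none for stage composition. Their stated power with 175 per arm (96, 92, 84 and 79%) recomputes to 96.3, 92.0, 84.8 and 79.9% with continuity correction, and all five sample sizes at 90% power (134, 164, 204, 230, 262 per arm) reproduce exactly.

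**Inputs.** From the documents: 175 resolved subjects trigger the interim (half of 350), 12 weeks of treatment, totals of 350 or 500. Assumed: r randomized per week, and a fraction d discontinuing evenly over the 12 weeks.

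**Composition if stage 1 is everyone resolved at the cut.**

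- In the last 12 weeks 12r subjects entered. On average half of their dropout has happened, so 6rd are resolved.
- The other 175 - 6rd subjects in stage 1 entered at least 12 weeks earlier.
- Discontinuer share in stage 1: s1 = [d(175 - 6rd) + 6rd]/175 = d + 6rd(1 - d)/175.
- Share in stage 2: (350d - 175 s1)/175, or (500d - 175 s1)/325 after an increase.
- Randomized at the cut: 175 - 6rd + 12r.

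Example, r = 10 and d = 0.15: s1 = 0.15 + 60 × 0.15 × 0.85/175 = 0.194; stage 2 = (52.5 - 33.9)/175 = 0.106; randomized = 175 - 9 + 120 = 286.

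| r per week (d = 15%) | Stage 1 | Stage 2, N = 350 | Stage 2, N = 500 | Randomized at cut | n/350 |
|---|---|---|---|---|---|
| 3.5 | 16.5% | 13.5% | 14.2% | 213.9 | 0.611 |
| 6 | 17.6% | 12.4% | 13.6% | 241.6 | 0.690 |
| 10 | 19.4% | 10.6% | 12.6% | 286.0 | 0.817 |
| 15 | 21.6% | 8.4% | 11.5% | 341.5 | 0.976 |

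At r = 10 the split is 13.1% against 6.9% for d = 10%, and 25.5% against 14.5% for d = 20% (N = 350). Simulated enrolments agree to within about 0.2 points. A constant-hazard version at 7 per week and 15% gives 18.1% against 11.9%. With stage 1 set by randomization order, both stages have 15.0%.

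**Type I error.** The test is two-sided at 5% (SAP 8.1.3). The simulation used 20,000 null trials per case, 7 per week, CHW weights of 0.5 and an assumed rule that raises N to 500 when conditional power is 50 to 90%. Monte Carlo standard error is 0.15 points.

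| Status-based cut | Rejection |
|---|---|
| Missing at random, 15% dropout in both arms | 5.1% |
| Discontinuers as nonresponders, 15% in both arms | 4.7% |
| Missing at random, 20% CR845, 10% placebo | 5.1% |
| Discontinuers as nonresponders, 20% and 10% | 5.2% |

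In the last case the mean z was -0.11 in stage 1 and +0.10 in stage 2; with randomization-order stages both were about 0.

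**Weight.** The intended value is 175/350 = 0.50. The literal n gives 0.69 at 6 per week and 0.82 at 10. At 15 per week I carry 0.97, because simulated accrual gave about 340 randomized (340/350).

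For 30% against 46% with 175 per arm, no increase and no continuity correction:

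- SE = √[(0.21 + 0.2484)/175] = 0.0512, so the total drift is 0.16/0.0512 = 3.126.
- Each 175-subject stage has drift 3.126/√2 = 2.211.
- The combined drift is 2.211(√w + √(1 - w)), where w = n/N.

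| w | Drift | Power, Φ(drift - 1.96) |
|---|---|---|
| 0.50 | 3.126 | 88% |
| 0.69 | 3.067 | 87% |
| 0.82 | 2.940 | 84% |
| 0.97 | 2.560 | 73% |

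With no increase, the adjusted log odds ratio reduces to r1 × stage 1 + (1 - r1) × stage 2. Half the subjects would then carry 69% to 97% of the estimate.

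**The case against.** The trigger says when the interim happens, not who is in stage 1. It can be read as the first 175 or so randomized, each followed to Week 12 or discontinuation. The n of SAP 8.2.2 and the split of SAP 8.2.3 point to randomization or enrolment, and a stage 1 of everyone enrolled before the cut has no enrichment either. The n could also mean the randomized subjects included in the interim analysis, which is about 175 and leaves the weight at 0.50. Part of protocol 8.4.1 is redacted and the IDMC charter is not public, so a membership rule may exist there. All of this stands, and it is why a biased cohort cannot be called the plan's definition. It does not remove the conflict among the visible sentences.

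A reader might also infer that selection on discontinuation invalidates the primary test. The documents do not support that. The selection rule is the same in both arms, the primary imputation assumes missing at random within arm, and the simulated error rate stays near 5%. The SAP also analyses the combined data without CHW and shows each stage, so a difference between stages would be visible.

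The size rests on accrual and dropout rates that the documents do not give. The gap is smaller at slow accrual and after an increase to 500.

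**Conclusion.** The point holds as an inconsistency with practical consequences. SAP 8.2.2, 8.2.3 and 11.1 do not agree on stage membership or on n.

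If stage 1 is everyone resolved at the cut, it is enriched for discontinuers at every accrual rate examined: about 16.5% to 21.6%, against 13.5% to 8.4% in stage 2 at N = 350, or 14.2% to 11.5% at N = 500. This assumes 15% dropout spread evenly and 3.5 to 15 randomized per week. It affects the interim sample-size decision, the stage-specific estimates and Sensitivity 1. It does not materially inflate type I error, under an assumed re-estimation rule because the actual one is not visible.

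Separately, pairing the literal n with a 175-subject stage 1 moves the weight from 0.50 to about 0.69 to 0.97 at 6 to 15 per week. Approximate power for 30% against 46% then falls from 88% to between 87% and 73%. This is a cheap improvement worth making before unblinding, not a flaw that invalidates the design.

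**What to change.** Use one rule everywhere:

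- Stage 1 is the first 175 subjects randomized, each followed to Week 12 or discontinuation. The interim is run when the last of them is resolved.
- Every later-randomized subject belongs to stage 2, whatever their status at the cut.
- Use n = 175 (r1 = 0.5) in the CHW weight and in the adjusted estimate.
- Use the same split for the before-and-after-interim display, and report discontinuation by stage and arm.

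The wording changes in SAP 8.2.2, 8.2.3 and 11.1, in protocol 8.4.1, 8.7.1 and the Statistical Appendix, and in the IDMC charter. The other cost is time: the interim waits for about 6rd more subjects, which is 6rd/r = 6d weeks, or 0.6, 0.9 and 1.2 weeks at 10, 15 and 20% dropout.

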11.2 DSMB

The operation of the DSMB will be governed by a charter that will describe the group's meeting frequency, procedures, and requirements for reporting its observations to the sponsor.

Safety data will be reviewed on an ongoing basis by the sponsor and a DSMB (for details see Safety Surveillance Plan and Safety Management Plan). In order to actively monitor subject safety, a prospective approach will be taken to collect and analyze certain adverse events designated as adverse events of special interest.

These analyses are outside the scope of this document.

12. CHANGES TO THE ANALYSES PLANNED IN THE PROTOCOL

- The protocol defines clinically notable vital signs based on values observed at the visit and on change from baseline. The definition was updated to remove the criteria based on change from baseline since it was deemed not necessary.
- The protocol states that Akaike information criterion will be used to select the appropriate covariance matrix structure for the MMRM analysis. The SAP uses an unstructured covariance matrix structure as the first choice. Should the model fail to converge, a compound symmetric covariance matrix will be used instead.
- Throughout the protocol, MMRM analyses state that random subject effects will be used, but also provide R-side matrix structures, rendering the random effect (GZ matrix) unnecessary. Random effects have therefore been removed throughout.
- The protocol states that the ShOWS scores on Discontinuation Period Days 1, 2, and 3 and days after Day 3 will be compared between treatment groups using an ANCOVA model. Because scores taken on Day 1 of this period will be included in the model as the subject's baseline score, this analysis was revised to compare ShOWS scores on Discontinuation Period Days 2, 3, and 4, 5, 6 and average assessment on days after Day 6. Additionally, the MMRM analysis was dropped, a categorical analysis was added for OOWS, and text clarifying the OOWS collection times was added.
- The protocol states that adverse events and vital signs potentially related to withdrawal that occur during the 2-week Discontinuation Period will be compared to the adverse events and vital signs reported during the 2-week period preceding the Discontinuation Period. Per the SAP, no comparison to the 2-week period prior to the Discontinuation Period will be made.
- The rules of mapping the early termination visit and the unscheduled visits into a scheduled visit based on visit windows were clarified in the SAP. The protocol states that if 2 or more evaluations occur in the same visit window, the evaluation closest to the target visit day will be selected for inclusion in the analysis. This was revised to select the non-missing value in the order of scheduled visit, early termination visit, and the unscheduled visits.
- The Double blind Discontinuation and Double blind Discontinuation Safety Populations were added.
- For the 5-D Itch Scale and the Skindex-10 Scale, the protocol specifies an MMRM analysis only. The SAP expands the analysis of these endpoints to include ANCOVA models with MI as the main analysis of these secondary variables, per Food and Drug Administration guidance. The MMRM model will be included as a sensitivity analysis.
- Analyses to identify possible cases of withdrawal from AEs added.

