8.9.4 Discontinuation Period Additional Assessments

Baseline ShOWS and OOWS will be the scores collected on the dialysis day on Day 85 (Double-blind EOT/Early Termination) (Table 2). Only patients who have a baseline ShOWS and OOWS will be included in the analysis.

Summary statistics for the daily ShOWs and the OOWS collected at each dialysis visit, including number of non-missing observations, mean, standard deviation, median, minimum, and maximum median of ShOWS and OOWS will be tabulated by treatment group. Figures for the overall mean scores over time will also be presented.

The ShOWS scores on discontinuation days 1, 2, 3, and >3 will be analyzed to compare the treatment groups at each visit, using an Analysis of Covariance (ANCOVA) model, with treatment group and baseline value as a covariate. The OOWS scores will be analyzed using a similar ANCOVA model at each day of collection. In addition, between-treatment group comparisons over the overall 2-Week Discontinuation Period will be performed using an MMRM with treatment group, discontinuation day, and treatment group-by-day interaction as fixed effects, baseline value as the covariate, and patient as a random effect. An unstructured covariance matrix will be used to model the covariance of within-patient scores. These analyses will be performed based on all postbaseline scores using only the observed cases without imputation of missing values.

Exploratory analyses may be performed, depending on sample size, for the subgroup of patients who also stop taking concomitant opioid medications during the 2-week Discontinuation Period.

Adverse events (AEs) and vital signs potentially related to withdrawal that occur during the 2-week Discontinuation Period will be identified based on a blinded review of the data, and will be summarized by randomized treatment group, and compared to the 2-week period prior to discontinuation.

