8.2.4.3 Key Secondary Analyses

5-D Itch Scale and the Skindex-10 Scale

The 5-D Itch Scale and the Skindex-10 Scale scores will be analyzed only at Week 12 using an analysis of covariance (ANCOVA). The model will contain treatment as fixed effects, with baseline score and the randomization stratification variables as covariates. The baseline 5-D total score and the Skindex-10 total score will be defined as the value collected on Day 1, prior to randomization. This is a change from the final protocol dated 21DEC2017 and is being implemented to address the FDA advice received on 10JAN2019 stating that “*the analysis [of continuous efficacy endpoints] should be based on only data from one timepoint (e.g. Week 12); however, modeling approaches using all timepoints may be used as supportive analyses.*”

Additionally, subjects who discontinue treatment but continue on study and have 5-D and Skindex-10 scores recorded will have these scores censored following discontinuation of treatment; missing data rules will apply to these censored values as though they had missing values/ dropped out from the study entirely.

For each domain in each questionnaire, missing values at Week 12 will be imputed using an MI approach, assuming that subjects who discontinue double-blind treatment early would have similar 5-D Itch and Skindex-10 scores as other subjects in their respective treatment arm that have complete data. All available visits will be included in the MI to

better inform the Week 12 imputed results. The MI approach will proceed as follows, using all ITT subjects (that is, it will not be split into IA subjects and post- IA subjects):

- Intermittent missing scores will first be imputed using the Markov Chain Monte Carlo (MCMC) method implemented with the SAS MI procedure, which is appropriate for non-monotonic missing data.
- The monotone missing values will then be multiply imputed with the SAS MI procedure using the monotone regression method.
- For each stage, MI will be performed within treatment group with covariates for baseline score, both randomization stratification factors, and all non-missing visit scores for each domain of the questionnaire. Should convergence issues occur due to small cell size for the categorical covariates at either stage, they will be removed from the model.
- Twenty imputations will be performed for each domain.

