10.5 ShOWS and OOWS

Short Opiate Withdrawal Scale

SOWS-Gossop (or ShOWS) is a self-administered scale for grading opioid withdrawal symptoms over a 24-hour period. This subject-rated scale consists of 10 items, scored from 0 (none) to 3 (severe); the total score is calculated as the sum of the individual items (total score range 0–30). If any individual values are missing, the total will be missing. The higher the score, the greater the severity of associated withdrawal.

The ShOWS will be presented as a paper worksheet to be filled by each subject, at home on non-dialysis days and at the dialysis unit on dialysis days, at a similar time of the day for a given subject during the 2-week Discontinuation Period (during which no study drug will be administered).

Objective Opiate Withdrawal Scale

The OOWS-Handelsman contains 13 physically observable signs, rated present (score of 1) or absent (score of 0); the total score is calculated as the sum of the individual items (total score range 0–13), based on a timed period of 5 to 10 minutes of observation of the subjects by a rater. If any individual values are missing, the total will be missing. Higher total scores will indicate more severe withdrawal signs. The rater will be a qualified staff member who will be trained by the Sponsor.

The OOWS will be presented as a paper worksheet to be filled by a qualified staff member at the dialysis unit on dialysis days (Discontinuation days 1,3,5,8,10 and 12), at similar time of the day for a given subject during the 2-week Discontinuation Period (during which no study drug will be administered).

Analyses

Summary statistics for the daily ShOWs and the OOWS collected at each dialysis visit, including number of non-missing observations, mean, standard deviation, median, minimum, and maximum of ShOWs and OOWS, will be tabulated by treatment group for the Double-blind Discontinuation Safety Population and Double-blind Discontinuation Population. Figures for the overall mean scores over time will also be presented. The ShOWS scores on Discontinuation Period Days 2, 3, 4, 5, 6, and average assessment on days after Day 6 will be analyzed to compare the treatment groups at each visit, using an ANCOVA model, with treatment group and baseline (Day 85) value as a covariate.

[figure not shown]

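### The ShOWS and OOWS ANCOVAs leave out the randomization strata, and with the protocol's MMRM dropped neither scale keeps a modelled whole-period contrast

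*SAP*

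**What the plan says.** Protocol 8.9.4 plans two layers of between-arm analysis for the withdrawal scales. The first is day by day, "using an Analysis of Covariance (ANCOVA) model, with treatment group and baseline value as a covariate". The second covers the period as a whole: "between-treatment group comparisons over the overall 2-Week Discontinuation Period will be performed using an MMRM". Its terms are treatment group, discontinuation day and "treatment group-by-day interaction as fixed effects, baseline value as the covariate, and patient as a random effect". Neither layer contains the stratification factors.

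SAP 10.5 keeps the first layer, "using an ANCOVA model, with treatment group and baseline (Day 85) value as a covariate". For ShOWS this gives six models: Discontinuation Days 2, 3, 4, 5 and 6, and the average of the later days. For OOWS it gives a similar model on Days 1, 3, 5, 8, 10 and 12. The OOWS average after Day 6 gets summary statistics only. The categorical OOWS display, which includes the maximum over the whole period, consists of counts and percentages.

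SAP 12 records the loss of the second layer: "Additionally, the MMRM analysis was dropped". The reason given in that bullet, that the Day 1 score serves as baseline, explains the new choice of ShOWS days. It does not explain dropping the MMRM.

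Elsewhere the SAP does adjust for the strata. The 5-D Itch and Skindex-10 ANCOVA in SAP 8.2.4.3 is fitted "with baseline score and the randomization stratification variables as covariates". The MMRMs in 8.2.4.3 and 8.2.5.1 and the Cochran-Mantel-Haenszel test for PGIC in 8.2.5.3 also use them.

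**The concern.** Protocol 7.1 says the Discontinuation Period is there to assess physical dependence, and ShOWS and OOWS are its dedicated scales. Two features of the plan weaken what they can show.

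- **Strata.** Randomization is stratified by two factors. A model that ignores them leaves any variance they explain in the residual, so the intervals are somewhat too wide. On a safety question, lost sensitivity leans towards finding no difference.
- **Whole-period contrast.** A reader who wants one estimate with an interval for the two weeks will not find one on either scale. The gap is larger for OOWS, where no average of any kind is modelled.

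There is also a plain slip. SAP 10.5 still lists an OOWS ANCOVA on Discontinuation Day 1.

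**Working it through.** The documents give no SD, between-day correlation, margin or power for ShOWS or OOWS, so there is no stated figure to reproduce. Every R² and correlation (rho) below is an assumption, shown over a range.

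**1. Cost of omitting the strata.** Let R² be the share of residual variance, after treatment and the Day 85 score, that the two strata explain. With strata close to balanced between arms, the interval that ignores them is too wide by 1/√(1 − R²) − 1.

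| Assumed R² | Calculation | Excess width |
|---|---|---|
| 2% | 1/√0.98 − 1 | 1.0% |
| 5% | 1/√0.95 − 1 | 2.6% |
| 10% | 1/√0.90 − 1 | 5.4% |

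**2. What is modelled on each scale (SAP 10.5).**

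| | Single days | Late average | Whole period |
|---|---|---|---|
| ShOWS | Days 2–6, ANCOVA | Days after Day 6, ANCOVA | none |
| OOWS | Days 1, 3, 5, 8, 10, 12, ANCOVA | summary statistics only | counts of the maximum only |

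ShOWS is collected daily from Day 85 to Day 98, which is 14 days. Day 85 is baseline, so 13 follow-up days remain (Discontinuation Days 2–14), of which 8 fall after Day 6.

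**3. What an OOWS period average would add.** The post-baseline OOWS visits are Days 3, 5, 8, 10 and 12. With equal correlation rho between visits, the SE of their mean relative to one visit is √((1 + 4·rho)/5).

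- rho 0.3: √(2.2/5) = 0.66
- rho 0.5: √(3.0/5) = 0.77
- rho 0.7: √(3.8/5) = 0.87

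At the planned 175 per arm, an upper bound for the analysed sets, the difference detectable with 80% power at one visit is (1.96 + 0.84)·√(2/175) = 0.30 residual SD. For the five-visit mean it is 0.20, 0.23 and 0.26 SD at rho 0.3, 0.5 and 0.7. This gain assumes that the effect persists through all five visits.

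**4. What a period average would hide.** If a constant effect is present at only k of the five visits, the z-value of the mean relative to one affected visit is (k/5) divided by the ratio in step 3. For k = 2 (Days 3 and 5 only) this is 0.4/0.663 = 0.60, 0.4/0.775 = 0.52 and 0.4/0.872 = 0.46. For a ShOWS effect lasting 3 of 13 days, the ratio is (3/13)/√((1 + 12·rho)/13) = 0.39, 0.31 and 0.27. A short withdrawal is therefore better seen in the day-level results.

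**5. Day-specific precision.** The day-level results lose little when the MMRM is dropped. In a simulation of 1,500 trials (175 per arm, five visits, rho 0.5), the last-visit treatment estimate from ANCOVA had the same SD as the MMRM estimate with complete data. Its SD was about 2% larger with 10% dropout and 3–4% larger with 20%. What is lost is the pooled estimate.

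**6. The OOWS model on Day 1.** Table 2 of the protocol (footnote b) equates Discontinuation Day 1 with Day 85, and SAP 3 makes Day 85 the baseline for both scales. The outcome and the covariate are then the same number for every patient. The fitted covariate slope is 1, and the treatment effect and residual are zero by construction. SAP 12 removed this problem for ShOWS but not for OOWS, so five of the six OOWS models are informative.

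**The case against.** The strongest reply is that little is lost. The change is listed openly in SAP 12, and both documents say that the SAP prevails. SAP 3 makes p-values outside the multiplicity algorithm descriptive. The SAP also adds dependence analyses: OOWS categories, blinded review of withdrawal-type adverse events, and a population restricted to patients treated for 12 weeks with recent dosing. It resolves the early days more finely than the protocol did. All of this stands, and it limits the point to a modest improvement.

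A reader might also infer four stronger things that the documents do not support.

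- **That both scales are now compared only day by day.** ShOWS keeps an ANCOVA on the average after Day 6, which covers 8 of the 13 follow-up days.
- **That ShOWS loses much precision.** The fair comparator for a 13-day mean is that retained 8-day average. Under equal correlation the 8-day SE, √((1 + 7·rho)/8), is 0.62, 0.75 and 0.86 of a single day at rho 0.3, 0.5 and 0.7. The 13-day mean gives 0.59, 0.73 and 0.85, so the late average is only about 5%, 2% and 1% less precise. If correlation decays with time (lag-1 values of 0.5 to 0.95), the gap is 23% down to 4%. The late average does not cover Days 2–6.
- **That dropping the MMRM caused the strata to be lost, or raised the risk of false positives.** The protocol's ANCOVA and MMRM had no strata either. The protocol also had day-level tests, and restoring the MMRM would remove none of them.
- **That the strata must matter because one of them concerns falls, confusion or gait.** No document gives their relation to either scale, and the models already adjust for the patient's own Day 85 score. That is why R² is only assumed here.

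**Conclusion.** The point holds, at modest size. The ShOWS and OOWS ANCOVAs omit the two randomization factors, out of line with the SAP's 5-D Itch, Skindex-10, NRS and PGIC analyses. The cost is about 1% to 5.4% in interval width for an assumed R² of 2% to 10%. The omission dates from the protocol.

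Separately, the SAP removes without a stated reason the only model-based comparison over the whole Discontinuation Period. This matters most for OOWS, where a five-visit mean would have an SE of 0.66 to 0.87 of a single visit at assumed correlations of 0.3 to 0.7. That benefit depends on a lasting effect, so the period average belongs beside the day-level results as support and should not replace them as the headline.

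The OOWS model on Discontinuation Day 1 is an error whatever is assumed. The documents do not support a claim that the dependence assessment is invalid or that error rates have risen.

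**What to change.** 1. In SAP 10.5, add the two randomization stratification variables to the ShOWS and OOWS ANCOVAs, with the convergence fallback for small cells that the SAP uses in its imputation models.
2. As a supportive analysis, restore the protocol's MMRM on scores after Day 85, with treatment, day, treatment-by-day, the Day 85 score and the two strata. Report the treatment difference averaged over the period with its 95% confidence interval, for OOWS above all. Keep the day-level results, because a two-week mean dilutes a short effect. If the MMRM is not restored, SAP 12 should say why.
3. Delete Discontinuation Day 1 from the OOWS ANCOVA days and keep it in the summary statistics.

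The cost is SAP wording and one or two tables, with no new data. Fitting should be feasible. An unstructured matrix has 5·6/2 = 15 parameters for OOWS and 13·14/2 = 91 for ShOWS, against 12·13/2 = 78 in the weekly NRS MMRM already planned. The SAP's compound-symmetric fallback can be reused. Adding the strata has no real downside. The risk in the second change is that a diluted average is read as the main answer, which the supportive label is meant to prevent.
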